**Group 2: SwallowSTRONG® device-facilitated I-PRO therapy plus compensatory treatments:**

[figure not shown]
Isometric tongue strengthening will be completed using the SwallowSTRONG® device (see Figure 1).

This device hand-held instrument provides numeric readout of pressure (hPa) and digital feedback of performance. It consists of a short cord (approx. 10 inches), which is attached to a small digital touch screen display. The 4-sensor array is custom-molded to the hard palate to ensure consistent placement.

Tongue press exercises consist of pressing the tongue against the sensors. Isometric exercises will focus on the anterior and posterior sensor. Subjects will be given a target pressure value for both the anterior and posterior sensor locations for which to aim during strengthening. Visual feedback on the display will signal the subject that they have attained their target pressure goal.

Prior to initiation of the strengthening regimen, baseline one repetition maximum (1RM) lingual pressures will be obtained at the anterior and posterior sensors independently by gathering 3 tongue press trials at each site that differ by less than 5% to adjust for variability in these measures. Subjects will take the SwallowStrong® device home with them and will complete 20 repetitions of the exercise (10 repetitions at the front sensor; 10 repetitions at the back sensor), three times per day on three days per week for twelve weeks. It will take approximately 10 minutes to complete 20 repetitions of the exercise resulting in about 30 minutes total for each home exercise session. During week one of the regimen, the target value of each repetition will be 60% of the 1RM. For the remaining eleven weeks of the program, the target value will be increased to 80% of the 1RM. These values of 60% and 80% were chosen based on previous work that employed progressive resistance training for the limbs and lingual musculature with healthy elders and patients post-stroke. At weeks three, five, seven, nine, and eleven, the baseline will be re-measured by phone and the 80% target value re-calculated. In addition, check-in phone calls also will be scheduled the other weeks of the study period.

**Figure 1**

## **Visits**

**Baseline visit only:**

After the informed consent process has been completed but prior to videofluoroscopic examination of swallowing, each participant will complete a medical history questionnaire to ensure they meet inclusion/exclusion criteria. This questionnaire will include items related to current medical status, medical history, and medication usage. UW medical records also will be referenced to ensure the subject's eligibility for participation. As part of this screening, patients will undergo a urine pregnancy test to ensure they are not pregnant prior to participation. The Mini-Mental Status Examination (MMSE) will be administered only at baseline as a common examination of cognitive functioning. In addition, the Barthel index will be administered to assess severity of impairments in activities of daily living. For each patient, a form with demographics as well as a medication list will be filled out. These questionnaires and tests will take approximately 45 minutes to complete. For those subjects randomly assigned to Group 2, during this baseline visit, it also will take approximately 30 minutes to train the participant on how to do and record the exercises properly. In addition to the consent process and these procedures that will occur only at the baseline visit, the procedures described below will also be completed at this visit. The entire baseline visit will last about 2.5 hours. For the baseline visit and 8 week visit, videofluoroscopic examination of swallowing will need to be completed before the other procedures outline below as the outcome of that examination will determine the patient's continued participation in the study. If s/he does not meet criteria for dysphagia on the videofluoroscopic swallowing exam, s/he will either not be randomized to a study group (at baseline visit) or will not continue participation past the 8 week point (if dysphagia has resolved).

*Measures at each assessment point (baseline, 8 weeks, and 12 weeks):* The 8 week and 12 week visits will last about 90 minutes per session. The study includes up to 3 sessions which will require up to 7 hours in total. In addition if in Group 2, participation in the home exercises will last about 10 minutes per session, 9 sessions per week for up to 12 weeks, which will require up to 18 hours total.

*Quality of Life Questionnaire:* Each subject will complete the Swal-QOL, a validated questionnaire focused on swallowing-related quality of life. It comprises 10 multi-item scales, 2 general scales, and a 14-item symptom battery. Care will be taken so that patients will not receive the tool from their treatment clinician, thereby avoiding potential bias in their responses. This questionnaire will take 10-15 minutes to complete.

*Dietary Questionnaire:* Each subject will complete a questionnaire detailing his/her quantity and variety of nutritional intake. From these responses, a Functional Oral Intake Scale (FOIS) score will be derived. The FOIS is a validated scale that represents level of oral intake from no oral intake (enteral feeding) to total oral intake with no restrictions. This questionnaire will take 10-15 minutes to complete.

*Isometric tongue pressure measurement:* One repetition maximum (1RM) isometric lingual pressures will be measured at the front and back sensors of the device. Subjects will be instructed to press with their tongue as hard as possible against the front and back sensors positioned on the palate. Three 1RM values will be collected for both front and back sensors, with a 20-second rest between each measurement.

*Saliva collection and analyses:* Saliva samples will be collected from patients at each study visit. We will attempt to schedule study visits between the hours of 12pm and 2pm when saliva

production is at its peak for the day. Before collection, patients will be asked to rinse their mouth thoroughly with distilled water to remove any food debris. Saliva will be collected under an unstimulated condition (expectorating into a tube for 5 minutes without swallowing or moving the tongue or jaw) as well as a stimulated condition (expectorating into a tube for 5 minutes while moving the jaw in a chewing motion to the rhythm of 70 beats per minute set with a metronome). The order of conditions will be randomized for each patient. A rest period of 10 minutes will be provided between collection conditions. Salivary flow rate will be determined by recording the volume of saliva produced in 5 minutes under each condition. Samples will be aliquoted into two separate tubes (per collection condition) and placed immediately on ice. One aliquot per condition will be transported to the laboratory of [name] in the Department to Food Science. In [name] laboratory, rheological and tribological analyses of the samples will be completed to characterize the fluid flow properties of saliva as well as its lubrication qualities. The protocol for collection, transport, and discarding of saliva samples has been approved by the Office of Biological Safety (#B00000105). Procedures outlined in that approved protocol will be followed to ensure proper handling of samples. Another aliquot per condition will be stored in the freezer within the laboratory of [name], PhD in the Department of Medicine for later completion of enzyme-linked immunosorbent assay to quantify levels of Substance P in the samples. [name] lab is approved for analyses and storage of human samples (biohazardous materials).

*Videofluoroscopic (VFS) assessment:* The KayPENTAX® Digital Swallowing Workstation (DSW) will be used to capture full resolution fluoroscopic images in real time (30 frames per second). Each subject will be seated and viewed in the lateral plane. The image intensifier will be focused on the lips anteriorly, posterior pharyngeal wall posteriorly, hard palate superiorly, and just below the upper esophageal sphincter (UES) inferiorly. The oral cavity and pharynx will remain in view after the swallow for 2 seconds to assess oropharyngeal residue. Subjects will swallow each of the following boluses twice: 3mL thin liquid, 10mL thin liquid, sips of thin liquid from a cup (approximately 10-15mL each sip), 3mL semi-solid boluses, and barium-infused cookie boluses. Subjects will also swallow one barium pill taken either with thin liquid barium from a cup or in approximately 3mL of semi-solid barium depending on how the patient normally takes pills. Finally, subjects will swallow two 3mL semi-solid boluses in the anterior-posterior view to allow for assessment of symmetry of the swallow. This will result in a total of 13 swallows. Based on the barium given during these 13 swallows, a total of 56 ml of liquid barium sulfate solution (Varibar Thin, Bracco), up to 12ml of pudding barium sulfate solution (Varibar pudding, Bracco), two barium sulfate infused cookies (Wanda's Barium Cookies, 1.5" in diameter); and a barium pill will be ingested. These boluses will be clinician-administered via teaspoon (3-ml) or self-administered via cup (10-ml, natural sips), or self-determined (portion of or whole cookie). If aspiration occurs, that bolus condition will be terminated once the cause of the aspiration is determined to provide clinical remediation. This VFS protocol is consistent with standard practice at the UW facilities. This assessment will take about 35 minutes.

*Swallowing Pressures:* Swallowing pressures will be measured using three small air-filled bulbs (Kay Pentax, Lincoln Park NJ) mounted on a silica strip attached longitudinally with adhesive anteriorly to posteriorly at the midline of the hard palate. The Kay system allows time-linking of swallowing pressure data with videofluoroscopic images.

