## **Intervention**

Participants who meet criteria for dysphagia on the videofluoroscopic swallowing examination will be randomly assigned into one of two groups: 1) a control group that will be receiving compensatory treatments only or 2) 12-week DF I-PRO therapy *plus* compensatory treatments, such as thickened liquids and/or postural strategies during natural swallowing activities for 12 weeks. Patients will be enrolled and trained in DF I-PRO therapy by [name] who regularly uses the SwallowSTRONG®-facilitated I-PRO therapy in clinical practice or a UW Voice and Swallowing clinician involved in this study who has been adequately trained in DF I-PRO therapy. Regardless of the treatment group to which a subject is randomized, they will be evaluated in the hospital at baseline and 8-week time points. If a patient in either group no longer meets criteria for dysphagia (Penetration-Aspiration Scale score of 3 or higher OR a rating of 2 on the Residue scale in any location) on the 8-week videofluoroscopic swallowing examination, s/he will no longer continue participation in the study. If a patient in either group remains dysphagic at the 8-week visit, s/he will continue participation in the study through the 12-week assessment point. [name] or a UW Voice and Swallowing clinician will conduct the 8 and 12 week assessments.

**Group 1: Compensatory treatments only:** This group will receive standard swallowing intervention, which is identified by the SLP as appropriate to treat the patient's dysphagia and is common clinical practice. This group is not receiving experimental therapy. Their therapy may include: 1) modifying the foods the subject eats or the fluids s/he drinks; 2) changing his/her posture when eating or drinking (for example, by a simple chin tuck) or using a swallowing maneuver while eating or drinking; 3) having him/her eat more slowly or in a quiet environment to make swallowing easier and safer; or 4) performing range of motion or vocal exercises for

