protocols will be recorded only by this code number. The link connecting the subject and code number will be password-protected stored separately in electronic format on the password-protected hospital network and only the PI ([name]) will have access. Only the approved project research staff ([name], [name]) will have access to the coded study data. All information about the subject will be treated confidentially and will not be revealed unless required by law. All HIPAA regulations pertaining to protection of participants and eliminating identification will be followed. Data will be de-identified at the close of the study. Any breach of confidentiality will immediately be reported to the IRB. Individual medical records will be accessed twice during the one year duration of this study: once by [name] initially to confirm the subjects' eligibility for the study and then again at the end of the study (one year point) to determine number of pneumonia diagnoses and hospital readmissions for the same number of months pre- and post-enrollment. Results of study-related procedures performed solely for research purposes (not standard of care) will not be placed in the subjects' medical record.

*Videofluoroscopic Swallowing Assessment:* Subjects are at risk for aspirating during the VFS assessment. If aspiration occurs during the VFS assessment, the particular bolus condition will be terminated once the cause of the aspiration is determined. Following completion of the study protocol, compensatory approaches to treatment (e.g., postures, diet modification) may be attempted in order to determine which strategies are most effective in reducing or eliminating the occurrence of airway penetration and/or aspiration, thereby ensuring safety with swallowing for patients in both treatment groups.

Subjects will be exposed to radiation exposure equivalent to one to two years of background radiation (less than 2.5 minutes) during the videofluoroscopic swallowing study. The risks of that amount are considered to be very small, and there is no indication of harmful effects to an individual. Subjects will not be included if they are pregnant. Radiation exposure during the VFS assessment will be limited as much as possible through attention to time restraints and adherence to ASHA's Guidelines for Speech-Language Pathologists Performing Videofluoroscopic Studies. Protective apparel with lead-shielding (lead apron, thyroid shield) will be worn at all times.

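### The only written pregnancy test is at baseline, but the study schedules further fluoroscopy at 8 and 12 weeks

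*Combined protocol and SAP*

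**What the plan says.** **Pregnancy.** Current pregnancy is an exclusion criterion. In the Visits section, under *Baseline visit only*, screening includes a urine test: "patients will undergo a urine pregnancy test to ensure they are not pregnant prior to participation". The same paragraph refers to "these procedures that will occur only at the baseline visit", so the test belongs to that visit alone. The radiation paragraph of Data Safety and Monitoring adds: "Subjects will not be included if they are pregnant".

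**Number of exams.** The videofluoroscopic assessment is described under "Measures at each assessment point (baseline, 8 weeks, and 12 weeks"), and "The study includes up to 3 sessions". The Intervention section makes the third visit conditional: "If a patient in either group remains dysphagic at the 8-week visit", participation runs on to week 12; otherwise it ends at week 8.

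**Exposure.** Data Safety and Monitoring gives one figure, "equivalent to one to two years of background radiation (less than 2.5 minutes) during the videofluoroscopic swallowing study". It also provides for limiting exposure, following professional guidelines and wearing a lead apron and thyroid shield. These provisions are written for the assessment in general.

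**Entry routes.** Under Subjects, the usual recruit is a patient who needs the swallow study as routine care; consent and screening come first. A second route admits patients who have recently had a swallow study, and they consent after it.

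**The concern.** The protocol treats pregnancy as a reason not to expose a subject to study radiation, and it thought the matter important enough to require a test. That test is done once, while the exposure recurs 8 weeks later and, for some, 12 weeks later. A subject who conceives after baseline would meet no written check before either repeat exam. The lower age limit is 21, and nothing restricts entry by childbearing potential.

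The later exams are also the ones that the study itself schedules. The baseline exam is one the patient needs clinically, whereas the 8-week exam applies to both groups by protocol, and the 12-week exam to everyone still dysphagic.

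A second, smaller matter is that the exposure statement does not say whether it describes one exam or the whole trial. A reader therefore cannot tell how much radiation the section calls very low risk. What is at stake is an avoidable safety gap for a few people and an incomplete risk description, not the validity of the trial's estimates.

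**Working it through.** **Step 1. Set exams against checks.**

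| Time | Videofluoroscopy | Who has it | Written pregnancy check |
|---|---|---|---|
| Baseline, usual route | Yes, clinically required | All | Urine test before the exam |
| Baseline, recent-exam route | Already done before consent | Those entering this way | None by the study can precede it |
| 8 weeks | Yes, scheduled by the study | All who continue | None |
| 12 weeks | Yes, scheduled by the study | Those still dysphagic at 8 weeks | None |

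The regular check-in calls and the weekly safety contact do not mention pregnancy. The exclusion criterion and the sentence in the radiation paragraph both concern entry. So up to two study-scheduled exams have no written check before them.

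The second row also shows a conflict. The Visits section places screening, including the test, after consent and before fluoroscopy. Under Subjects, some patients consent after fluoroscopy. Both cannot hold for those entrants.

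**Step 2. The exposure figure.** It cannot be reproduced: the documents give no effective dose, no dose per minute and no background rate. The only arithmetic available is multiplication by the number of exams, k, on the assumption that the figure is per exam:

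years = k × (1 to 2); minutes < k × 2.5

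| k | Years of background | Minutes |
|---|---|---|
| 1 | 1 to 2 | < 2.5 |
| 2 | 2 to 4 | < 5 |
| 3 | 3 to 6 | < 7.5 |

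**Step 3. Which k applies.**

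- Subject who stops at week 8: two exams in all (2 to 4 years, < 5 minutes), of which the study adds one (1 to 2 years, < 2.5 minutes).
- Subject who reaches week 12: three in all (3 to 6 years, < 7.5 minutes), of which the study adds two (2 to 4 years, < 5 minutes).

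The study-added counts treat the baseline exam as routine care, and assume that a recent clinical exam is used in place of a new one for those who enter that way.

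If the figure is already the whole-trial total, it stays at 1 to 2 years and < 2.5 minutes, and nothing needs multiplying.

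**Step 4. Which reading is likelier.** The wording is singular. Each exam has 13 swallows, with the view held for 2 seconds after the swallow. Over one exam, 150 s / 13 = 11.5 s per swallow. Over three exams, 150 s / 39 = 3.8 s per swallow, including those 2 seconds. The per-exam reading fits better, but this is inference and does not settle the matter.

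**The case against.** The strongest case on the other side has five parts.

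- **Other safeguards remain.** A reader might infer that all the radiation safeguards cover only the first exam. The documents do not support that: limits on exposure time, professional guidelines and lead shielding are not confined to baseline. This stands, and later exams are not unprotected. The text does not say who wears the shielding, however, and the protocol lists non-inclusion of pregnant subjects alongside it, so shielding was evidently not thought to make the pregnancy safeguard redundant.
- **The figure is not shown to be wrong.** A reader might infer that the stated exposure is three times too low. It is given for one swallow study. Read per exam, it is not too low, and only the cumulative figure is missing. Read as a total, it is complete. This stands in full.
- **The baseline exam is clinical care.** Counting it as trial exposure would overstate what the study adds. This stands, and the study adds at most two exams on the assumptions above. It does not close the gap, because the exams without a check are the ones the study schedules.
- **Checks may exist elsewhere.** Hospital radiology may ask about pregnancy, and the consent pages are not available for review. So the most that can be said is that no check is written in the protocol text.
- **Few people are affected.** The Background says that the vast majority of strokes occur after age 65, and planned enrolment is 40. This stands and keeps the point minor.

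**Conclusion.** The point holds in a limited form. The protocol relies on excluding pregnant subjects as one of its radiation safeguards, but its only written pregnancy test is confined to baseline. No written check precedes the study-scheduled exam at 8 weeks or, for those still dysphagic, at 12 weeks. For subjects who enter after a recent swallow study, the study's test cannot precede the first exam either.

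The exposure figure needs a label, not a correction. On the assumption that it is per exam, the study adds up to 2 to 4 years of background (< 5 minutes), or 3 to 6 years (< 7.5 minutes) if all three exams are counted. The factor of three is a maximum that needs both attendance at week 12 and inclusion of the routine-care exam.

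Severity is minor. Few subjects can be affected, and power, error rates and estimates are untouched. The point rests on the protocol text as available, without the consent form or local radiology procedures.

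**What to change.** 1. Reconcile the recruitment text, the exclusion criteria, the Visits section and the radiation paragraph so that the pregnancy safeguard applies before each study-scheduled fluoroscopy. One way is to list the existing urine test among the procedures at the 8- and 12-week visits, ahead of the exam, for those to whom it applies. If another check is already in use, cite it there.
2. Acknowledge that for patients entering after a recent swallow study the first exam precedes consent, and amend the statement that screening comes before fluoroscopy accordingly.
3. In the radiation paragraph, say whether 1 to 2 years of background (< 2.5 minutes) is per exam or a total. If it is per exam, give both the amount the study adds (up to 2 to 4 years, < 5 minutes) and the amount over all three exams (3 to 6 years, < 7.5 minutes), and identify the baseline exam as routine care.

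The cost is at most two extra urine tests for each of a few women, a few amended sentences and a less favourable stated exposure. The sample size and the analyses do not change.

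### At week 8 the swallow study that decides continuation must precede SWAL-QOL and the dietary questionnaire, so unmasked subjects can answer them knowing or inferring their result

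*Combined protocol and SAP*

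**What the plan says.** The order of procedures is set under Visits, in the text on the baseline visit. It applies to the baseline and week-8 visits, where "videofluoroscopic examination of swallowing will need to be completed before the other procedures outline below as the outcome of that examination will determine" whether the subject carries on. A subject who no longer meets the criteria at week 8 "will not continue participation past the 8 week point (if dysphagia has resolved"). The Intervention section has the same rule.

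The procedures that follow are introduced as "Measures at each assessment point (baseline, 8 weeks, and 12 weeks"). The first two are:
- SWAL-QOL, described as "a validated questionnaire focused on swallowing-related quality of life";
- the dietary form: "Each subject will complete a questionnaire detailing his/her quantity and variety of nutritional intake". The FOIS score is derived from these answers.

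One safeguard against response bias is stated, and it concerns SWAL-QOL only: "Care will be taken so that patients will not receive the tool from their treatment clinician, thereby avoiding potential bias in their responses".

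Under Data Safety and Monitoring, once the protocol swallows are finished, "compensatory approaches to treatment (e.g., postures, diet modification) may be attempted in order to determine which strategies are most effective".

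No order is stated for the week-12 visit.

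**The concern.** SWAL-QOL is a self-report by people who know which treatment they had. The week-8 swallow study tells the subject, or lets the subject guess, whether swallowing has recovered and whether the study is over for them. Answers given minutes later may reflect that news as well as the preceding weeks of eating and drinking.

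If one arm has more resolved cases, more of its subjects answer after good news, and part of the week-8 difference in SWAL-QOL would come from the order of the visit. Were resolution commoner with therapy, the shift would favour Hypothesis 2a. Adjustment for age, gender and baseline score, as planned for Aim 2, would not remove it, and it cannot be corrected once the data are collected.

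The sponsor plainly wants unbiased answers, but the safeguard covers who hands over the form and not when it is completed.

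**Working it through.** **What the sections establish together**

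1. *Order.* The Visits rule covers week 8, and both questionnaires are listed after it. On the plan as written, they follow the swallow study at week 8.
2. *Masking.* Under Intervention, device therapy plus compensatory treatment is compared with compensatory treatment alone, with no sham. The only blinding described (Data Reduction and Analysis) is of the clinicians who measure the recordings.
3. *Access to the result.* No section says when the subject is told, and none says the result is held back. It decides continuation at that visit. A subject may also infer it: aspiration ends a bolus condition, and compensatory strategies may be tried after the swallows.
4. *Use of the data.* SWAL-QOL and FOIS are secondary outcomes. Week 8 enters two of the three changes modelled for Aim 2 (baseline to 8 weeks, and 8 to 12 weeks).
5. *Need for the order.* At week 8 everyone attending is already randomized, analysis is by intention to treat, and those who resolve leave only after that visit. The stated reason does not require the questionnaires to wait.

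**Size**

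The plan gives no figure for SWAL-QOL. Its one quantitative statement, the power table for lingual pressure, does not bear on the point but serves to check the method. A two-sided two-sample t-test at 5% with 15 per group and SD 100 hPa gives 75.3%, 56.2%, 35.5% and 18.5% for differences of 100, 80, 60 and 40 hPa. The table states 75%, 56%, 35% and 18%, so it reproduces.

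For the illustration, let g be the between-arm difference in the proportion resolved at week 8, and d the shift in score from knowing that dysphagia has resolved, taken as equal in both arms. Then:

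added group difference = g × d

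Both inputs are assumptions.
- In points on a 0-100 scale: 0.20 × 5 = 1.0, and 0.30 × 10 = 3.0.
- In SD units, over a wider range: 0.10 × 0.25 = 0.025 SD, and 0.40 × 0.5 = 0.20 SD.

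With 15 per group and no true effect on SWAL-QOL, a two-sided 5% t-test would reject in about 5.05% of trials at 0.025 SD, 5.8% at 0.10 SD and 8.3% at 0.20 SD. The difference detectable with 80% power at this size is about 1.06 SD. If g = 0, the added difference is zero.

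**Which visits and comparisons are exposed**

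- *Baseline.* Every randomized subject has met the dysphagia criteria, and the result precedes randomization. Between-arm bias is not expected.
- *Week 8.* The result can differ by arm. This is where the exposure lies.
- *Week 12.* No order is set. A difference in order from week 8 common to both arms would largely cancel between arms, but not in the comparison of 12 with 8 weeks (Hypothesis 2b). The 1 to 3 points do not describe that comparison, because subjects who resolve at week 8 have no 12-week answers.

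**The case against.** The strongest reply is that disclosure is inferred. A reader might take the plan to say that subjects are told their result before they fill in the forms. It does not. The passage on compensatory strategies says only that they may be tried, and does not mention disclosure. This stands, and it limits the point to what the plan permits.

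Second, the size is assumed throughout and is small even if accepted, in a pilot that can detect only about 1 SD. The mechanism also needs a real difference in resolution: with a common shift it amplifies a genuine effect on swallowing and does not create one from nothing. This stands too. It argues for modest weight, but the shift would be systematic and more subjects would not average it away.

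Third, a reader might infer that the 8-versus-12-week comparison definitely mixes two orders. The plan's silence on week 12 is not a different order. Conditions may differ, and no more can be said.

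Fourth, FOIS rests on reported intake, which a test result minutes earlier is less likely to alter than answers on fear or burden. It is the less plausible part of the concern.

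Fifth, putting questionnaires first at every visit cannot work. Under Subjects (Recruitment Process), patients with a recent swallow study consent after it, so research forms cannot precede it. This rules out a blanket baseline rule but leaves weeks 8 and 12 untouched.

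**Conclusion.** The point holds for week 8. The order is explicit, subjects are unmasked, and nothing prevents SWAL-QOL from being answered with the result known or guessed. The effect on the between-arm difference is of unknown size. The 1 to 3 points rest on an assumed 5 to 10 point shift, an assumed 20 to 30 percentage point gap in resolution, and an equal shift in both arms. On the wider assumed range, the false-positive rate for SWAL-QOL rises from 5% to at most about 8%.

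The documents do not support reading this as proof that results are disclosed first, as a between-arm bias at baseline, or as a known change of order at week 12. It concerns secondary outcomes only. It is worth correcting because the bias is avoidable, the sponsor already seeks to prevent bias of this kind, and the remedy is nearly free.

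**What to change.** Amend the ordering sentence under Visits so that at weeks 8 and 12 SWAL-QOL and the dietary questionnaire are completed first; at week 8 the swallow study then precedes all remaining procedures. This also gives the two visits the same conditions for the questionnaires. Withholding the result until the forms are complete would be a weaker alternative, since a subject could still infer it from the examination.

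At baseline the same order may be adopted for consistency where the swallow study follows consent. The text should exempt subjects whose swallow study came before consent. The plan already has a medical history questionnaire completed before the baseline swallow study, so the sequence is workable.

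**Cost.** At weeks 8 and 12 there is no added procedure or visit time. If adopted at baseline, each subject who then fails the dysphagia criteria spends 20 to 30 minutes on the two forms (10 to 15 minutes each). Enrolment allows for 40 − (2 × 15) = 10 such subjects. If all 10 fail after completing the forms, the total is 10 × 20/60 = 3.3 hours to 10 × 30/60 = 5 hours.
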